7.2.2.7 Cardiac assessments

7.2.2.7.1 Electrocardiogram (ECG)

A standard 12 lead ECG will be performed

- at screening
- pre-dose, on D1 of every cycle. For Cycle 1 Day 1 pre-dose ECG, the QTcF value must be within eligibility criteria prior to study drug treatment.
- Surgical group (group 2) : pre-dose on D1, and on the day of surgery
- at the EOT visit

[figure not shown]
A standard of 12-Lead ECG that monitors QTcF interval, heart rate, PR interval, uncorrected QT interval, and QRS duration will be performed as indicated in in [Table 7-1](#).

[figure not shown]
Interpretation of the tracing must be made by a qualified physician at the site and documented on the ECG eCRF. Each ECG tracing should be labeled with the study number, patient initials (where regulations permit), patient number, date, and kept in the source documents at the study site. Clinically significant abnormalities present when the patient signed informed consent should be reported on the Relevant Medical History/Current Medical Conditions eCRF. Clinically significant findings must be discussed with the Novartis Medical Monitor prior to enrolling the patient in the study. New or worsened clinically significant findings occurring after informed consent must be recorded on the AE eCRF.

[figure not shown]

[figure not shown]

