1.2.1.2.3 Clinical pharmacokinetics

In Study BGJ398X2101, full PK profiles were obtained on Day 1, Day 15 and Day 28 after the first dose of study drug. As this study is ongoing, all data presented are current as of 02 September 2012 (refer to the Investigator Brochure for further details).

At 5 and 10 mg/day, plasma concentrations of BGJ398 were low (< 3.3 ng/mL) and frequently below the lower limit of quantification. Exposure (C_{max} and AUC) was measurable in all treated patients starting at 20 mg/day.

The median apparent T_{max} value across all dose levels tended to be 2-3 hours post-dose. At the MTD (125 mg q.d.), the C_{max} and AUC₀₋₂₄ were ~111 ng/ml and ~817 h.ng/ml on Day 1 and ~318 ng/mL and ~5301 h.ng/mL on Day 15.

The inter-patient variability was moderate to high for BGJ398 and % coefficient of variation (% CV) ranged from 30 – 110 % for dose groups 20-150 mg on Day 15. The exposure differed significantly between some patients at the same dose levels. At the MTD dose of 125 mg, high inter-individual variability was observed on Day 1 (101% and 94% CV for C_{max} and AUC₀₋₂₄, respectively). This inter-individual variability appeared to decrease on Day 15 (35% and 41 % in CV% for C_{max} and AUC₀₋₂₄).

Accumulation was observed with daily dosing. The mean AUC₀₋₂₄ ratios between Cycle 1 Day 1 and Cycle 1 Day 15 ranged from 1.5 to 6.5, which indicates some change in BGJ398 exposure following multiple dosing. At doses of 60 mg and above, most individual patients showed increased exposure on Day 15 following multiple dosing (~1.5 – 13 fold relative to Day 1 exposure). Very limited data are available for patients who received continuous dosing for 28 days without dose interruptions (8 patients at doses 60 mg and above, only 7 patients with PK data). In most of these patients who received uninterrupted dosing, a further increase in exposure beyond Day 15 was observed. This is based on either AUC₀₋₂₄ exposure on Day 28 or comparing predose samples after Day 15 in these patients. Refer to the BGJ398 Investigator's Brochure for further details.

In most patients, across all study days and dose levels, active metabolites were measurable. As a percentage of parent exposure, BHS697 was detected at ~10-15% and BQR917 at < 10%.

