- A third or subsequent reduction (to 50 mg) in dose may be allowed if the patient is clearly benefiting from study treatment (i.e., stable disease, partial response, or complete response) but is experiencing adverse events that prevent continued treatment at the already reduced dose.

Table 6-2 Dose reduction table

Dose level	BGJ398	
Dose level 0	125 mg	Starting dose
Dose level -1	100 mg	
Dose level -2	75 mg	
Dose level -3	50 mg	Allowed only if patients is clearly benefiting from study treatment, but is experiencing AE that prevent continued treatment at dose level -2

Table 6-3 Criteria for interruption and re-initiation of BGJ398 treatment

Worst Toxicity CTCAE using the current active CTCAE version	Recommended Dose Modifications any time during a cycle of therapy
Cardiac disorders	
Cardiac - Prolonged QTcF interval	
Grade 1 and 2 : QTcF ≥ 481msec and ≤ 500 msec (asymptomatic)	
Maintain dose level of BGJ398
 
 ● ECG assessments should be performed for 2 additional cycles at the same frequency as in cycle 1, or as clinically indicated. If ECG assessments show no QTcF ≥ 481 msec, for subsequent cycles ECG monitoring will be performed as per visit schedule. ● If ECG assessments are still abnormal (QTcF ≥ 481 msec and ≤500 msec), then ECG monitoring must continue at the same frequency as in cycle 1 for all subsequent cycles.

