Grade 3 : QTcF > 500msec as identified on the ECG by the investigator	
 ● Hold BGJ398. ● Monitor patient with hourly ECGs until the QTcF has returned to baseline. ● Perform further monitoring as clinically indicated. ● Exclude other causes of QTcF prolongation such as hypokalemia, hypomagnesaemia and decreased blood oxygenation. ● Patients should receive appropriate electrolyte replacement and should not receive further BGJ398 until electrolytes are documented to be within normal limits. 
Once the QTcF prolongation has resolved, patients may be re-treated at one lower dose level at the investigator's discretion
 
 ● ECG assessments should be performed for 2 additional cycles at the same frequency as in cycle 1 or as clinically indicated 
 ● If ECG assessments show no QTcF ≥ 481 msec, for subsequent cycles ECG monitoring will be performed as per visit schedule. ● If ECG assessments are still abnormal (QTcF ≥ 481 msec and ≤500 msec), then ECG monitoring must continue at the same frequency as in cycle 1 or as clinically indicated, for all subsequent cycles ● Patients who experience recurrent QTcF ≥ 500msec after one dose reduction will be discontinued from study. 
NB: If ventricular arrhythmia or Torsades de Pointes is observed in a patient, he/she will be discontinued from the study.

Worst Toxicity CTCAE using the current active CTCAE version	Recommended Dose Modifications any time during a cycle of therapy
Cardiac disorders - others Grade ≥ 3 , or congestive heart failure ≥ 2	Discontinue patient from study treatment.
Investigations-Hematology	
ANC decreased (Neutropenia) Grade 3 (ANC $< 1.0 - 0.5 \times 10^9/L$) Grade 4 (ANC $< 0.5 \times 10^9/L$)	Hold dose of BGJ398 until resolved to CTCAE Grade ≤ 1 or baseline, then 
 • If resolved in ≤ 7 days, maintain dose level of BGJ398 • If resolved in > 7 days, \downarrow 1 dose level of BGJ398. Hold dose of BGJ398 until resolved to CTCAE \leq Grade 1, \downarrow 1 dose level of BGJ398.

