	Category	Reference to section	Molecular pre - screening	Screening	Pre-Surgical Treatment	Day of Surgery	Cycle 1					Cycle 2				Cycle 3	Subsequent cycles	End of study treatment	30 day Follow up	Disease Progression	Survival follow up			
			Screening Phase		Surgical phase (Group 2)			Treatment Phase														Follow-up		
Day of cycle				-28 to -1	1	5-10	6-11	1	2	8	15	22	1	8	15	22	1	22	1	22				
Chemistry	D	7.2.2.5.2		X				X	X	X	X	X	X	X	X	X	X	X	X	X	X			
Coagulation	D	7.2.2.5		X				If clinically indicated																
Urinalysis (microscopic or macroscopic)	D	7.2.2.5.3		X				If clinically indicated																
Pregnancy test	D	7.2.2.5		X				X					X				X		X		X			
Ophthalmologic assessment	D	7.2.2.8		X				X			X		X				X		X		X			
Tumor response per RANO v1.0 (* : within 72 hours of surgery)	D	7.2.1		X			X*	First post baseline scan occurs cycle 3 day 1; subsequent scans occur every 8 weeks until unacceptable toxicity or disease progression, whichever occurs first														X		X
Surgery	D	4.1					X																	
Study drug administration		6.1			Continuous from day 1 till day of surgery			Continuous on a 3 weeks on 1 week off schedule																
12-Lead ECG (*pre-dose)	D	7.2.2.7		X	X*		X	X*					X*				X*		X*		X			

[figure not shown]

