2.8.4 Other safety data**2.8.4.1 ECG and cardiac imaging data**

12-lead ECGs including PR, QRS, QT, and QTcF, will be obtained central/local for each subject during the study. ECG data will be read and interpreted centrally locally

The number and percentage of subjects with notable ECG values will be presented.

- QT, or QTcF
 - New value of > 450 and ≤ 480 ms
 - New value of > 480 and ≤ 500 ms
 - New value of > 500 ms
 - Increase from Baseline of > 30 ms to ≤ 60 ms
 - Increase from Baseline of > 60 ms
- HR
 - Increase from baseline $>25\%$ and to a value > 100 bpm

- Decrease from baseline >25% and to a value < 50 bpm
- PR
 - Increase from baseline >25% and to a value > 200 ms
 - New value of > 200 ms
- QRS
 - Increase from baseline >25% and to a value > 120 ms
- New values of QRS > 120 ms

A listing of notable ECG values will be produced. In the listing, the assessments collected during the post-treatment period will be flagged.

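### Table 6-3 answers QTcF prolongation with the routine ECG schedule, and no scheduled in-cycle ECG is taken after a dose on a dosing day

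*Protocol*

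**What the plan says.** **Routine schedule.** Protocol Section 7.2.2.7.1 lists ECGs at screening and at the end-of-treatment (EOT) visit. Within the cycles, its instruction is "pre-dose, on D1 of every cycle. For Cycle 1 Day 1 pre-dose ECG, the QTcF value must be within eligibility criteria prior to study drug". For surgical patients it adds "Surgical group (group 2) : pre-dose on D1, and on the day of surgery". The row of Table 7-1 labelled "12-Lead ECG (*pre-dose") matches. Its treatment-phase marks fall only on Day 1 of each cycle, all starred as pre-dose.

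**After QTcF prolongation.** Table 6-3 (Section 6.2.1) has two branches.
- For 481 to 500 msec without symptoms, the dose is kept and two further cycles are monitored at the Cycle 1 frequency or when clinically indicated. If the abnormality persists, "then ECG monitoring must continue at the same frequency as in cycle 1 for all subsequent cycles". If it clears, monitoring goes back to the visit schedule.
- For more than 500 msec, drug is held and ECGs are hourly until QTcF is back to baseline. On re-treatment, "ECG assessments should be performed for 2 additional cycles at the same frequency as in cycle 1 or as clinically indicated", with the same two outcomes afterwards.

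**Analysis.** SAP Section 2.8.4.1 states: "The number and percentage of subjects with notable ECG values will be presented". The categories include new QT or QTcF values above 480 and above 500 ms, and increases from baseline above 60 ms. SAP Section 2.1.1 defines the on-treatment period as first dose to 30 days after last dose. Protocol Section 10.5.3.4 adds a shift table from baseline to worst on-treatment ECG result.

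**The concern.** There are two linked problems. First, the response to a prolonged QTcF is written as a step up in monitoring with a possible step down later, yet both steps point to the same schedule. A site that follows the text exactly schedules nothing extra for a patient who has just shown prolongation.

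Second, the in-cycle tracings are all pre-dose on Day 1, whereas the protocol's own pharmacokinetics put peak exposure elsewhere: "The median apparent T_{max} value across all dose levels tended to be 2-3 hours post-dose" (Section 1.2.1.2.3), with higher levels on Day 15 than on Day 1. The interruption and re-initiation rules in Table 6-3 are driven by QTcF values, and the SAP counts tracings taken after the week off as on-treatment. A low count of notable values could then be read as reassurance about QTcF during dosing, which those tracings did not sample.

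**Working it through.** The plan gives no figure to reproduce here. The check is a reading of the schedule plus simple counting.

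**1. Count the in-cycle ECGs.** Table 7-1 has 13 treatment-cycle visit columns: Cycle 1 Days 1, 2, 8, 15, 22; Cycle 2 Days 1, 8, 15, 22; Cycle 3 Days 1, 22; later cycles Days 1, 22. The ECG row is marked in 4 of them, each a Day 1 and each pre-dose.

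**2. Time since last dose.** Dosing is on Days 1 to 21 (Section 2.2). The next Day 1 is Day 29, and 29 − 21 = 8 days after the last dose, with 7 dose-free days. The Cycle 1 Day 1 tracing precedes the first cycle dose and serves as an eligibility check. The ±3-day visit window in Section 7.1 can shift these days, but a pre-dose tracing stays pre-dose.

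**3. Coverage over six cycles.** Dosing days: 6 × 21 = 126. Scheduled in-cycle ECGs: 6, of which 1 comes before any cycle dose and 5 follow a week off. Scheduled ECGs after a dose on a dosing day: 0.

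**4. Scheduled ECGs near drug outside the cycles.**
- Group 2, day of surgery: planned after 5 to 10 days of daily dosing, with the last dose within 24 hours of surgery (Section 4.1). At the expected 2:1 ratio this is 34/3, about 11 patients, once each.
- EOT: the visit is within 14 days of the last dose (Section 4.1), so 0 to 14 days.

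**5. Compare routine and triggered monitoring.**

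| Step in Table 6-3 | Scheduled ECGs per cycle |
|---|---|
| Cycle 1 frequency (the reference) | 1, Day 1 pre-dose |
| Two further cycles after prolongation | 1, Day 1 pre-dose |
| All later cycles if still abnormal | 1, Day 1 pre-dose |
| Return to visit schedule if clear | 1, Day 1 pre-dose |

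The difference between triggered and routine is 1 − 1 = 0. The Group 2 pre-surgical ECGs do not change this, because Sections 4.1 and 7.1.3 start Cycle 1 with the first dose after surgery.

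**6. What goes beyond routine.** Two things do: ECGs done when clinically indicated, and hourly ECGs once QTcF is above 500 msec. The continuing step for persistent 481 to 500 msec carries no clinically indicated clause of its own in Table 6-3, although Section 7.1 allows such assessments generally.

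**7. Exposure by day.** At 125 mg in the continuous-dosing study (Section 1.2.1.2.3), Day 15 over Day 1 is 5301/817 = 6.5 for AUC0-24 and 318/111 = 2.9 for Cmax. The part of the cycle with accumulated exposure has no scheduled tracing.

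**The case against.** **Sparse ECGs are defensible for this drug.** Sections 6.3.2 and 6.3.3 say there is no current evidence of an effect on conduction or ECG intervals. In vivo safety pharmacology showed no electrocardiographic effect (Section 1.2.1.1.2). The hERG IC50 of 1121 ng/mL is 1121/318 = 3.5 times the Day 15 Cmax on total drug, and more on free drug given about 98% binding. None of the four dose-limiting toxicities was a QT event. This stands, and it limits the weight of the point. It does not explain a triggered step that equals the routine one.

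**A reader might infer that QTcF on drug is never observed.** The documents do not support that. The day-of-surgery ECG, possibly the EOT ECG, clinically indicated ECGs and the hourly ECGs all exist.

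**A reader might infer that drug is washed out by Day 1, so that notable counts must be near zero.** That does not follow either. The protocol gives no half-life. If kinetics were linear with accumulation ratio R, the level 8 days after the last dose relative to the 24-hour trough would be (1 − 1/R)^7. The stated range of R from 1.5 to 6.5 gives about 0.05% to 31%, and the 125 mg ratio sits at the upper end. Linearity is itself an assumption.

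**Some ECG text may have been removed.** Section 7.2.2.7.1 has gaps in the public copy, and Section 7.1 has a blacked-out passage beside the visit windows. The point therefore concerns the visible text. The ECG row of Table 7-1 is visible, however, and shows Day 1 only.

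**Conclusion.** The point holds in two parts. The first needs no pharmacology: Table 6-3 and Table 7-1 cannot both mean what they say, because monitoring at the Cycle 1 frequency is the routine schedule. The step-up adds zero scheduled ECGs and the step-down removes none. The second is descriptive: in the cycles, no scheduled ECG is post-dose on a dosing day, so the SAP's notable-value counts will rest largely on pre-dose tracings taken after a week off.

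The conclusion assumes an uninterrupted patient and that the visible schedule is complete. It does not say that the drug prolongs QT, how much drug remains on Day 1, or when ECGs should be done. It is worth correcting because it bears on patient safety and on how the ECG tables are read. It does not touch the primary endpoint.

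**What to change.** - **Protocol:** reconcile Table 6-3 with Table 7-1 and Section 7.2.2.7.1, so that monitoring triggered by QTcF prolongation can be told apart from routine monitoring. State whether any ECG is intended on dosing days. The choice of timing is the sponsor's.
- **SAP Section 2.8.4.1:** report notable QTcF values by time since last dose, so that tracings after the week off are not read as QTcF at on-drug exposure. Dose dates are already on the dosing record.

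**Cost:** one amendment to three places in the protocol and a little more analysis work. Days 8 and 15 of Cycles 1 and 2 are already visits. From Cycle 3 the table has only Days 1 and 22, and Day 22 is the first day off drug, so an ECG on any dosing day other than Day 1 would then need a new visit.

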7.2.2.8 Ophthalmologic assessments

[figure not shown]
Ophthalmologic examinations will be performed as indicated in [Table 7-1](#) and includes: visual acuity testing, slit lamp examination of the anterior eye segment, intraocular pressure (IOP), and fundoscopy. Additional examination methods such as specular microscopy (that enables a magnified, direct view of the corneal endothelium), corneal pachymetry, and dilated fundoscopy will be performed as clinically indicated.

8 Safety monitoring and reporting

8.1 Adverse events

8.1.1 Definitions and reporting

An adverse event is defined as the appearance of (or worsening of any pre-existing) undesirable sign(s), symptom(s), or medical condition(s) that occur after patient's signed informed consent has been obtained.

AEs which occur after signature of this consent will only be captured if they meet the definition of serious as outlined in [Section 8.2](#) and are reported to be causally related with study procedures (e.g., an invasive procedure such as biopsy). Once the main study ICF is signed, all AEs per the descriptions below will be captured in the Adverse Event CRF.

Abnormal laboratory values or test results occurring after informed consent constitute adverse events only if they induce clinical signs or symptoms, are considered clinically significant, require therapy (e.g., hematologic abnormality that requires transfusion or hematological stem cell support), or require changes in study medication(s).

Adverse events that begin or worsen after informed consent should be recorded in the Adverse Events CRF. Conditions that were already present at the time of informed consent should be recorded in the Medical History page of the patient's CRF. Adverse event monitoring should be continued for at least 30 days following the last dose of study treatment. Adverse events (including lab abnormalities that constitute AEs) should be described using a diagnosis whenever possible, rather than individual underlying signs and symptoms. When a clear diagnosis cannot be identified, each sign or symptom should be reported as a separate Adverse Event.

Adverse events will be assessed according to the Common Terminology Criteria for Adverse Events 4.03 version unless otherwise specified.

If CTCAE grading does not exist for an adverse event, the severity of mild, moderate, severe, and life-threatening, corresponding to Grades 1 - 4, will be used. CTCAE Grade 5 (death) will not be used in this study; rather, information about deaths will be collected through a Death form.

The occurrence of adverse events should be sought by non-directive questioning of the patient (subject) during the screening process after signing informed consent and at each visit during the study. Adverse events also may be detected when they are volunteered by the patient (subject) during the screening process or between visits, or through physical examination, laboratory test, or other assessments. As far as possible, each adverse event should be evaluated to determine:

1. The severity grade (CTCAE Grade 1-4)
2. Its duration (Start and end dates) or Ongoing at End of Study
3. Its relationship to the study treatment (Reasonable possibility that AE is related: No, Yes)
4. Action taken with respect to study or investigational treatment (none, dose adjusted, temporarily interrupted, permanently discontinued, unknown, not applicable)
5. Whether medication or therapy was given (no concomitant medication/non-drug therapy, concomitant medication/non-drug therapy)
6. Outcome (not recovered / not resolved, recovered / resolved, recovering / resolving, recovered / resolved with sequelae, fatal, unknown)
7. Whether it is serious, where a SAE is defined as in [Section 8.2.1](#).

All adverse events should be treated appropriately. If a concomitant medication or non-drug therapy is given, this action should be recorded on the Adverse Event eCRF.

Once an adverse event is detected, it should be followed until its resolution or until it is judged to be permanent, and assessment should be made at each visit (or more frequently, if necessary) of any changes in severity, the suspected relationship to the study treatment, the interventions required to treat it, and the outcome.

Progression of malignancy (including fatal outcomes), if documented by use of appropriate method (for example, as per RANO criteria for GBM), should not be reported as a serious adverse event.

Adverse events separate from the progression of malignancy (example, deep vein thrombosis at the time of progression or hemoptysis concurrent with finding of disease progression) will be reported as per usual guidelines used for such events with proper attribution regarding relatedness to the drug.

Whenever possible, a diagnosis should be reported instead of underlying signs and symptoms.

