8.2 Serious adverse events

8.2.1 Definitions

Serious adverse event (SAE) is defined as one of the following:

- Is fatal or life-threatening
- Results in persistent or significant disability/incapacity
- Constitutes a congenital anomaly/birth defect
- Is medically significant, i.e., defined as an event that jeopardizes the patient or may require medical or surgical intervention to prevent one of the outcomes listed above
- Requires inpatient hospitalization or prolongation of existing hospitalization,
- Note that hospitalizations for the following reasons should not be reported as serious adverse events:
 - Routine treatment or monitoring of the studied indication, not associated with any deterioration in condition
 - Elective or pre-planned treatment for a pre-existing condition that is unrelated to the indication under study and has not worsened since signing the informed consent
 - Social reasons and respite care in the absence of any deterioration in the patient's general condition
- Note that treatment on an emergency outpatient basis that does not result in hospital admission and involves an event not fulfilling any of the definitions of a SAE given above is not a serious adverse event

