8.2.2 Reporting

SAEs will only be reported if the event is suspected to be causally related to a study procedure as assessed by the investigator (e.g., an invasive procedure such as biopsy). SAEs will be followed until resolution or until clinically relevant improvement or stabilization. If the main ICF is not signed (molecular screen failure), SAE collection ends 30 days after the last study related procedure.

SAE collection starts at time of main study informed consent whether the patient is a screen failure or not.

To ensure patient safety, every SAE, regardless of suspected causality, occurring after the patient has provided informed consent and until at least 30 days after the patient has stopped study treatment must be reported to Novartis within 24 hours of learning of its occurrence.

Any SAEs experienced after this 30 days period should only be reported to Novartis if the investigator suspects a causal relationship to the study treatment. Recurrent episodes, complications, or progression of the initial SAE must be reported as follow-up to the original episode within 24 hours of the investigator receiving the follow-up information. An SAE

occurring at a different time interval or otherwise considered completely unrelated to a previously reported one should be reported separately as a new event.

Information about all SAEs is collected and recorded on the Serious Adverse Event Report Form; all applicable sections of the form must be completed in order to provide a clinically thorough report. The investigator must assess and record the relationship of each SAE to each specific study treatment (if there is more than one study treatment), complete the SAE Report Form in English, and send the completed, signed form by fax within 24 hours to the oncology Novartis Drug Safety and Epidemiology (DS&E) department.

Serious adverse events considered by the Investigator to be possibly related to a biopsy procedure will be indicated as such in the AE eCRF. This information will be followed for 30 days after the biopsy procedure.

The telephone and telefax number of the contact persons in the local department of Drug Safety and Epidemiology (DS&E), specific to the site, are listed in the investigator folder provided to each site. The original copy of the SAE Report Form and the fax confirmation sheet must be kept with the case report form documentation at the study site.

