14.3.2 Response/Progression Categories

Complete response (CR)

All of the following criteria must be met:

- a. Complete disappearance of all enhancing measurable and non-measurable disease sustained for at least 4 weeks. In the absence of a confirming scan 4 weeks later, this scan will be considered only stable disease.
- b. No new lesions.
- c. All measurable and non-measurable lesions must be assessed using the same techniques as baseline.
- d. Participants must be on no steroids or on physiologic replacement doses only.
- e. Stable or improved non-enhancing (T2/FLAIR) lesions
- f. Stable or improved clinically, for clinical signs and symptoms present at baseline and recorded to be disease related

Participants with non-measurable disease cannot have a complete response. The best response possible is stable disease.

Partial response (PR)

All of the following criteria must be met:

- a. Greater than or equal to 50% decrease compared to baseline in the sum of products of perpendicular diameters of all measurable enhancing lesions sustained for at least 4 weeks. In the absence of a confirming scan 4 weeks later, this scan will be considered only stable disease.
- b. No progression of non-measurable disease.
- c. No new lesions.
- d. All measurable and non-measurable lesions must be assessed using the same techniques as baseline.
- e. The steroid dose at the time of the scan evaluation should be no greater than the dose at time of baseline scan.
- f. Stable or improved non-enhancing (T2/FLAIR) lesions on same or lower dose of corticosteroids compared to baseline scan.

- g. Stable or improved, for clinical signs and symptoms present at baseline and recorded to be disease related clinically.

Participants with non-measurable disease cannot have a partial response. The best response possible is stable disease.

Progressive disease (PD)

The following criterion must be met:

- a. 25% increase in sum of the products of perpendicular diameters of enhancing lesions (over best response or baseline if no decrease) on stable or increasing doses of corticosteroids

and/or one or more of the following:

- b. Significant increase in T2/FLAIR non-enhancing lesion on stable or increasing doses of corticosteroids compared to baseline scan or best response following initiation of therapy, not due to co-morbid events (radiation therapy, demyelination, ischemic injury, infection, seizures, post-operative changes, or other treatment effects).
- c. Any new lesion

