- d. Clear clinical deterioration not attributable to other causes apart from the tumor (e.g., seizures, medication side effects, complications of therapy, cerebrovascular events, infection, etc.). The definition of clinical deterioration is left to the discretion of the investigator but it is recommended that a decline in the KPS from 100 or 90 to 70 or less, a decline in KPS of at least 20 from 80 or less, or a decline in KPS from any baseline to 50 or less, for at least 7 days, be considered neurologic deterioration unless attributable to comorbid events or changes in corticosteroid dose. Similarly, a decline in the Eastern cooperative Oncology Group (ECOG) performance scores from 0 or 1 to 2 or 2 to 3 would be considered neurologic deterioration, unless attributable to co-morbid events or changes in corticosteroid dose.
- e. Failure to return for evaluation due to death or deteriorating condition
- f. Patients with non measurable enhancing disease whose lesions have significantly increased in size and become measurable (minimal bidirectional diameter of ≥ 10 mm and visible on at least two axial slices that are preferably, at most, 5 mm apart with 0-mm skip) will also be considered to have experienced progression. The transition from a non measurable lesion to a measurable lesion resulting in progression can theoretically occur with relatively small increases in tumor size (e.g., a 9×9 mm lesion [non measurable] increasing to a 10×11 mm lesion [measurable]). Ideally, the change should be significant (> 5 mm increase in maximal diameter or $\geq 25\%$ increase in sum of the products of perpendicular diameters of enhancing lesions). In general, if there is doubt about whether the lesion has progressed, continued treatment and close follow-up evaluation will help clarify whether there is true progression.

Note that if there is uncertainty regarding whether there is progression, the patient may continue on treatment and remain under close observation (e.g., evaluated at 4-week intervals). If subsequent evaluations suggest that the patient is in fact experiencing progression, then the date of progression should be the time point at which this issue was first raised.

Stable disease (SD)

All of the following criteria must be met:

- a. Does not qualify for CR, PR, or progression.
- b. All measurable and non-measurable sites must be assessed using the same techniques as baseline.

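### Read together, protocol section 8.1.1 and Appendix 3 PD item (e) leave it unclear whether an unexplained death or deterioration between scans must be reported as an SAE

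*Protocol*

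**What the plan says.** **The exemption.** Protocol section 8.1.1 takes one class of event out of SAE reporting: "Progression of malignancy (including fatal outcomes), if documented by use of appropriate method (for example, as per RANO criteria for GBM), should not be reported". The sentence after it keeps "Adverse events separate from the progression of malignancy" reportable in the usual way, and gives deep vein thrombosis at the time of progression as one example.

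**What counts as progression.** Appendix 3, section 14.3.2, gives item (a), growth of enhancing lesions, and continues with "and/or one or more of the following". Item (d) in that list is "Clear clinical deterioration not attributable to other causes apart from the tumor". Item (e) is "Failure to return for evaluation due to death or deteriorating condition".

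**The general SAE rule.** Section 8.2.1 counts an event as serious if it "Is fatal or life-threatening", and also lists hospitalisation and other criteria. Section 8.2.2 requires that "every SAE, regardless of suspected causality, occurring after the patient has provided informed consent" and up to at least 30 days after the end of treatment be reported to the sponsor within 24 hours.

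**How deaths are otherwise captured.** Section 8.1.1 does not use CTCAE grade 5; instead, "information about deaths will be collected through a Death form". SAP section 2.8.1 summarises on-treatment deaths and all deaths, and lists every death in the Safety Set. Protocol section 10.5.3.2 tabulates only those deaths that are reportable as SAEs.

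**The concern.** The exemption names RANO as an acceptable way to document that an event is progression. One RANO criterion in this protocol, item (e), is met simply because the patient died or became too unwell to attend. It asks for no imaging and does not ask whether the tumour was responsible. An investigator who applies both texts as written can therefore classify an unexplained death as documented progression and conclude that it should not be reported as an SAE.

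An event of unknown cause is the kind for which a drug effect should not be assumed away. If it is not reported as an SAE, it may miss the 24-hour notification, the causality assessment that leads to SUSAR reporting, and the SAE tables. Type, frequency and severity of SAEs form a secondary endpoint (protocol Table 3-1). Section 8.6 provides for no data monitoring committee, so oversight depends on what investigators report and what the sponsor's team reviews.

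**Working it through.** The point is textual, and the plan states no figure to reproduce. The passages compare as follows.

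| Question | Text pointing to exempt | Text pointing to report |
|---|---|---|
| Is a fatal event reportable? | 8.1.1: not if it is progression documented by a suitable method such as RANO | 8.2.1 and 8.2.2: yes, whatever the suspected cause |
| Is one PD item sufficient? | 14.3.2: items joined by "and/or one or more of the following"; Table 14-4 requires any one criterion for PD | – |
| Does item (e) need a scan or attribution to tumour? | 14.3.2: neither is required | Item (d) requires attribution, but (e) does not repeat it |
| Is the event kept in as separate from progression? | Only if a separate event has been identified | 8.1.1: yes, once it is identified |

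Step by step:

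1. A patient dies of unknown cause before the next 8-weekly scan (section 7.2.1) and does not return. Item (e) is met.
2. One item is enough, so the patient has PD by the RANO criteria as Appendix 3 sets them out.
3. Section 8.1.1 accepts RANO as documentation and includes fatal outcomes, so its instruction is not to report an SAE.
4. The event is fatal, so 8.2.1 makes it an SAE and 8.2.2 requires a report within 24 hours.
5. Steps 3 and 4 conflict. The sentence on separate events does not settle it, because an unexplained death offers no identified separate event. No other passage ranks the two rules.

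The same chain applies to a patient who is alive but fails to return because of deterioration, if that deterioration meets another criterion in 8.2.1, such as hospitalisation.

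Sensitivity of the output: if all 34 planned patients are in the Safety Set, one death left out of the SAE table lowers the proportion with a fatal SAE by 1/34 = 2.9 percentage points. This is the effect of one event, not an estimate of how many there would be.

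**The case against.** The strongest reply is that the exemption should be read narrowly. It covers progression of malignancy that has been documented. In ordinary reading, an unexplained death is not documented progression, and the reference to fatal outcomes most naturally means deaths that follow progression already shown. Appendix 3 is written for judging antitumour response, and nothing in it says that it decides cause of death for safety reporting. Section 10.4.1 lists documented progression and death as separate PFS events. Section 8.2.2 gives an explicit general instruction to report. Table 7-1 also has visits well inside each 8-week interval, and deterioration seen at a visit can be judged under item (d), which does require attribution to the tumour.

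Much of this stands. It shows that reporting is a reasonable reading, perhaps the better one. It does not remove the conflict, because 8.1.1 names RANO as suitable documentation without excluding item (e).

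Three stronger inferences are not supported:

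- *That the protocol settles that such deaths need not be reported.* Non-reporting is one literal reading, and 8.2.2 opposes it.
- *That the gap can be sized from the 6 to 9 month median survival in protocol section 1.1.* That median concerns all-cause death in recurrent glioblastoma, whereas all glioma subtypes are eligible. It neither measures nor bounds the number of unexplained deaths.
- *That hERG inhibition in vitro (section 1.2.1.1.2) shows a cardiac risk that is being hidden.* The same section reports no in vivo effect on electrocardiographic parameters, and section 6.3.2 states that there is no current evidence of an effect on conduction or ECG intervals.

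Nor is a difference between the death tables and the SAE tables a defect in itself. Section 10.5.3.2 expects some deaths not to be SAEs.

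**Conclusion.** The concern holds as an unresolved conflict. Section 8.1.1 with PD item (e) permits an unexplained death or serious deterioration between scans to be treated as exempt, while 8.2.1 and 8.2.2 require it to be reported. The documents do not say which prevails, so sites may act differently. What is at risk is the 24-hour report, the causality and SUSAR assessment, and the SAE tabulation. The recording of the death is not at risk.

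The number of events affected cannot be derived from the documents. The conclusion rests on a literal reading of two provisions, and on the absence of any sentence limiting which PD items count for the exemption. It does not rest on any assumed toxicity of the drug. The correction is worth making because it is cheap and concerns safety reporting.

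**What to change.** Add one sentence to protocol section 8.1.1, along these lines: *PD item (e) of Appendix 3, taken alone, is not documented progression for the purpose of this exemption; an event that meets a criterion in 8.2.1, without progression documented under another PD item, is reported under 8.2.2.*

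Appendix 3 needs no change. PFS is unaffected: item (e) remains a PD criterion for efficacy, and death is already a separate PFS event in section 10.4.1.

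The cost is one sentence in a protocol amendment and a few more SAE reports, some of which will later be attributed to progression.
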